## 5.8 Criteria for Removal from Treatment

**5.8.1** At the beginning of cycle 1, if a patient requires more than 16 mg/day of dexamethasone to control cerebral edema by the time s/he is ready to begin treatment with 5-FC (and leucovorin, as indicated), then s/he will be considered neurologically unstable and will not continue with study treatment; however, the patient will still be evaluable for toxicity.

**5.8.2** Treatment will be held if a grade III or IV non-hematologic toxicity or a grade IV hematologic toxicity occurs that is at least possibly attributable to NSCs, 5-FC (and leucovorin, as indicated) or the combination. If the adverse event resolves as per criteria in section 6.3, then the patient will be allowed to proceed with the next treatment of NSCs and 5-FC (and leucovorin, as indicated), with dose modifications as outlined in section 6.3. If the adverse event does not resolve within the timeframe specified in section 6.3, or if more than 2 dose reductions are required, then study treatment will be stopped.

**5.8.3** Evidence of progressive disease.

**5.8.4** Patient needs any treatment not allowed by the protocol.

**5.8.5** A patient may always be removed from treatment whenever s/he wishes.

**5.8.6** If a patient needs to start full dose anticoagulation while receiving study treatment, s/he will be taken off study.

## 5.9 Study Stopping Rules

The study will be discontinued if i) the incidence of DLT level toxicities that are probably or definitely attributable to the NSCs and/or 5-FC (and leucovorin) in study patients exceeds 50% in more than 6 patients during cycle one of treatment, or ii) two grade 4 allergic reactions that are probably or definitely related to NSCs. Note death from tumor progression will be scored as a grade 5 toxicity (with very low

level of attribution—unlikely or not related), but only deaths occurring < 30 days from intracerebral administration of NSCs will be considered for the purposes of defining conditions for discontinuation of the study.

## 5.10 Additional Studies

Please see section 9.0 for further details about the correlative studies that will be performed.

## 5.11 Long Term Follow-Up

Patients will continue to be followed once they have finished active study treatment. They will be asked to participate in long term follow-up per the guidelines set forth by the FDA's Biological Response Modifiers Advisory Committee (BRMAC) that apply to gene transfer studies. Current recommendations from the BRMAC require a minimum of 15 years of follow-up. This long-term follow-up will consist of annual requests from the patient/patient's primary oncologist for clinical information regarding survival, as well as information pertaining to *de novo* cancer, neurologic, autoimmune, or hematologic disorders, and any adverse event that is at least possibly attributable to this study treatment. RCR testing will be part of the long-term follow-up of study patients and will be performed by analysis of DNA from whole blood by PCR for RCR-specific sequences at the following time points: pre-treatment, 3 months, 6 months, 1 year, and annually thereafter (see section 9.1.6).

# 6.0 Dose Delays/Modifications for Adverse Events

---

## 6.1 Toxicities to be Monitored

The study will use the NCI Common Terminology Criteria for Adverse Events (CTCAE) version 4.0. A copy of the version 4.0 can be downloaded from: <http://evs.nci.nih.gov/ftp1/CTCAE/About.html>

## 6.2 Expected Toxicities

### 6.2.1 Surgery toxicities

Bleeding, infection, headache, seizures, cerebral edema, pain, changes in neurologic function.

### 6.2.2 NSC toxicities

All toxicity studies to date in mice have shown no evidence of organ damage or tumorigenicity due to HB1.F3.CD. NSCs.

In the first-in-human study of this neural stem cell line, no grade 3 or 4 toxicities attributable to the NSCs were observed.

### 6.2.3 Chemotherapy toxicities

#### 6.2.3.1 5-FC

**Per the package insert for systemic 5-FC, the expected toxicities for 5-FC are:**

*Cardiovascular:* Cardiac arrest, myocardial toxicity, ventricular dysfunction.

*Ear and labyrinth disorders:* vertigo, hearing loss.

*Endocrine & metabolic:* Hypoglycemia, hypokalemia.

*Gastrointestinal:* Nausea\*, vomiting\*, abdominal pain\*, diarrhea\*, anorexia, dry mouth, duodenal ulcer, gastrointestinal hemorrhage, ulcerative colitis, enterocolitis\*.

*Hematologic:* Anemia, agranulocytosis, aplastic anemia, eosinophilia, leukopenia, pancytopenia, thrombocytopenia, and bone marrow aplasia including fatal cases.

*Hepatic:* Acute hepatic injury including hepatic necrosis with possible fatal outcome in debilitated patients, hepatic dysfunction, jaundice, bilirubin elevation, increased hepatic enzymes.

*Immune system disorders:* Allergic reaction.

*Nervous system disorders:* Ataxia, headache\*, paresthesia, parkinsonism, peripheral neuropathy, sedation, convulsions/seizure.

*Psychiatric:* Confusion\*, hallucinations\*, psychosis.

*Renal and urinary:* Azotemia, BUN elevation, crystalluria, renal failure, creatinine elevation.

*Respiratory:* Respiratory arrest, chest pain, dyspnea.

*Skin and subcutaneous tissue disorders:* Rash, pruritus, urticaria, photosensitivity, Lyell's syndrome (toxic epidermal necrolysis).

*Miscellaneous:* Fatigue, weakness, fever/pyrexia.

\*An asterisk signifies a common event according to Micromedex (updated July 2014).

#### 6.2.3.2 5-FU

**Per the package insert for systemic 5-FU, the expected toxicities for 5-FU are as follows, where the asterisk (\*) signifies a common event:**

*Cardiovascular:* myocardial ischemia, angina,

*Eye disorders:* photophobia, visual changes, lacrimation, lacrimal duct stenosis.

*Gastrointestinal:* stomatitis\*, esophagopharyngitis\*, diarrhea\*, anorexia\*, nausea\*, vomiting\*, gastrointestinal ulceration and bleeding.

*Hematologic:* leucopenia\* (nadir: days 9-14; recovery by day 30),, pancytopenia, thrombocytopenia, agranulocytosis, anemia.

*Immune system disorders:* anaphylaxis and generalized allergic reactions.

*Nervous system disorders:* acute cerebellar syndrome (which may persist following discontinuance of treatment), nystagmus, headache.

*Skin and subcutaneous tissue disorders:* alopecia\*, dermatitis (most commonly pruritic maculopapular rash)\*, dry skin; fissuring; photosensitivity, as manifested by erythema or increased pigmentation of the skin; vein pigmentation; palmar-plantar erythrodysesthesia syndrome, as manifested by tingling of the hands and feet followed by pain, erythema and swelling (hand-foot syndrome); nail changes (nail loss)

*Psychiatric:* disorientation, confusion, euphoria.

*Respiratory:* epistaxis.

*Miscellaneous:* thrombophlebitis.

Severe toxicity (such as stomatitis, diarrhea, neutropenia, and possibly neurotoxicity) associated with 5-FU has been attributed to deficiency of dipyrimidine dehydrogenase activity.

#### 6.2.3.3 Leucovorin

**As listed in the package insert (updated July 2014) the expected toxicities for oral and parenteral leucovorin are:**

*Allergic Reactions:* anaphylaxis and generalized allergic reactions

*Skin and subcutaneous tissue disorders:* hives (urticaria) associated with anaphylactoid reactions

Leucovorin with 5-FU:

Leucovorin can enhance the toxicity of 5-fluorouracil. Although the toxicities observed in patients treated with the combination of leucovorin plus 5-fluorouracil are qualitatively similar to those observed in patients treated with 5-fluorouracil alone, gastrointestinal toxicities (particularly stomatitis and diarrhea) are observed more commonly and may be more severe and of prolonged duration in patients treated with the combination.

#### **6.2.4 Microdialysis catheter toxicities**

Bleeding along the catheter track, infection localized to or clearly emanating from the catheter. Minor bleeding (less than 1 ml) has been observed in 3% of patients, and there have been no documented microdialysis catheter-related infections.

### **6.3 Dose Modifications/Delays/Start of Cycle Criteria**

#### **6.3.1 General Information**

6.3.1.1 The study will use the NCI Common Terminology Criteria for Adverse Events (CTCAE) version 4.0 to grade toxicities. A copy of the version 4.0 can be downloaded from:

<http://evs.nci.nih.gov/ftp1/CTCAE/About.html>

6.3.1.2 Whenever treatment is held pending resolution of toxicity to grade 1 or return to baseline, this criterion may also be met if the toxicity resolves to within 1 grade of the baseline value for a pre-existing laboratory abnormality. Baseline values are from screening assessments.

6.3.1.3 Study agents are always held together, regardless of the attribution of the toxicity.

6.3.1.4 NSC or 5-FC dose re-escalation and leucovorin restarting are never permitted in this study.

6.3.1.5 If, for the best interest of the patient, the investigator wants to hold the study agent(s) or dose reduce (including increasing the dose reduction) after an adverse event in a manner not outlined in Table 7.2.4, this is permissible following discussion with and written approval the Principal investigator.\*

6.3.1.6 For situations where a participant experiences a toxicity which the treating investigator feels is unlikely related to treatment with either study agent, but which requires hold or reduction of either agent according to Table 7.2.4, maintaining treatment or maintaining treatment dose is allowable per discussion with and written approval by the Principal Investigator.\*

6.3.1.7 For holds due to toxicities related to study agent(s), if the participant does not meet criteria to resume treatment within 14 days of the detection of the toxicity, the participant must permanently discontinue study treatment (all agents). However, if the participant is clearly benefiting from the study, the investigator may contact the Principal Investigator to determine if the participant can remain on study and at what dose level. Agreement of the Principal Investigator is to be documented in writing.\*

6.3.1.8 For holds for reasons other than treatment related toxicities, such as inclement weather or adverse events unrelated to study agents, if the participant does not meet criteria to resume treatment within 28 days of their last NSC administration, the study agent(s) may be restarted with written approval from the Principal Investigator, as long as there has been no significant evidence of disease progression during the treatment interruption.\*

6.3.1.9 Section 6.4 details resuming agent administration following a treatment hold.

\*The principal investigator will document assessment of the impact of these determinations on the study design, objectives and endpoints or risk to participants. If any modifications to the treatment plan might affect the study design, objectives, and endpoints, or impact the risk of participants, a single subject exception will be sought from the IRB. If the treating investigator is the principal investigator, the determination and the rationale for the determination will clearly be documented in the medical record.

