#### 3.1.4 Protocol-Specific Criteria

- 3.1.4.1 The patient must be in need of a craniotomy for tumor resection or a stereotactic brain biopsy for the purpose of diagnosis or differentiating between tumor progression versus treatment-induced effects following radiation therapy  $\pm$  chemotherapy.
- 3.1.4.2 Based on the neurosurgeon's judgment, there is no anticipated physical connection between the post-resection tumor cavity and the cerebral ventricles.
- 3.1.4.3 Patient must have adequate bone marrow function (defined as an absolute neutrophil count (ANC) of  $\geq 1500$  cells/mm $^3$  and platelet count  $\geq 100,000$  cells/mm $^3$ , adequate liver function with total bilirubin  $\leq 2.0$  mg/dl and AST (SGOT)  $\leq 4$  times the institutional upper limit of normal, and a serum creatinine  $\leq$  the institutional upper limit of normal.

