### **6.3.2 Start of Cycle Criteria**

In order to proceed with the next cycle of study treatment:

- adverse events (except for alopecia) that occurred in the preceding cycle must have improved to a CTCAE v 4.0 grade  $\leq 1$  (or within 1 grade of starting values for pre-existing laboratory abnormalities),
- ANC must be  $\geq 1500$  cells/mm $^3$ ,
- platelet count  $\geq 100,000$  cells/mm $^3$ , and

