Grade 4 Nervous System Disorder that is not attributable to tumor location or neurosurgery and is considered a least possibly attributable to NSCs, 5-FC, or leucovorin, or any combination and is not an immune response to study agents.		Hold until $\leq$ grade 1, then perform brain MRI. If objective evidence of clinical benefit, restart treatment with a dose reduction of NSCs and 5-FC by 25% of pre-hold dose, and, if patient is taking leucovorin, discontinue leucovorin.* If no objective evidence of clinical benefit is seen on MRI then, discontinue treatment.  *If the temporal association implicates NSCs or 5-FC (and leucovorin) rather than both/all agents, dose reductions may apply only to the implicated agent.
Other Unspecified Non-Hematologic Toxicities Considered Related Only to 5-FC (with Leucovorin)		
Grade 1		Maintain treatment
Grade 2		Maintain treatment
Grade 3		Hold study treatment until resolution to $\leq$ grade 1  For patients not taking leucovorin Restart treatment with a 25% decrease in 5-FC from the pre-hold dose.  For patients taking leucovorin First event: resume treatment at the same dose of NSCs and 5-FC, but permanently discontinue leucovorin. Additional events: resume treatment with a 25% dose reduction of 5-FC of the pre-hold dose.
Grade 4		Hold study treatment until resolution to $\leq$ grade 1  For patients not taking leucovorin Restart treatment with a 25% decrease in 5-FC from the pre-hold dose.  For patients taking leucovorin First event: resume treatment at the same dose of NSCs and 5-FC, but permanently discontinue leucovorin. Additional events: resume treatment with a 25% dose reduction of 5-FC of the pre-hold dose.
Other Unspecified Non-Hem Toxicities Considered Related Only to NSCs		
Grade 1		Maintain treatment
Grade 2		Maintain treatment
Grade 3		Hold until $\leq$ grade 1, then dose reduce NSCs by 25%; resume treatment with same dose of 5-FC and leucovorin.
Grade 4		Hold until $\leq$ grade 1, then perform brain MRI. If objective evidence of clinical benefit, restart treatment at pre-hold doses of 5-FC and leucovorin and a dose reduction of NSCs by 25% of the pre-hold dose of NSCs. If no objective evidence of clinical benefit is seen on MRI then discontinue treatment.
Other Unspecified Non-Hem Toxicities Considered Related to a Combination of NSCs and 5-FC (with Leucovorin)		
Grade 1	NSCs with	Maintain treatment

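### For a liver test or similar chemistry that was grade 2 at screening, the baseline allowance in 6.3.1.2 sets the release level at grade 3, the same grade that triggers the hold

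*Combined protocol and SAP*

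**What the plan says.** **Trigger.** Section 5.8.2 reads: "Treatment will be held if a grade III or IV non-hematologic toxicity or a grade IV hematologic toxicity occurs", where the event is at least possibly attributable to study treatment. It leaves resolution and dose changes to section 6.3.

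**Ordinary release.** A non-hematologic laboratory toxicity with no row of its own, such as a raised liver enzyme, falls under the catch-all rows of Table 6.3.4 ("Other Unspecified Non-Hematologic Toxicities Considered Related" to 5-FC only, with parallel rows for NSCs only and for the combination). At grades 3 and 4 these rows hold treatment until the event is grade 1 or less.

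**Alternative release.** Section 6.3.1.2 covers holds of this kind ("Whenever treatment is held pending resolution of toxicity to grade 1 or return to baseline") and adds that "this criterion may also be met if the toxicity resolves to within 1 grade of the baseline value for a pre-existing laboratory abnormality". It also fixes the reference point: "Baseline values are from screening assessments".

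**Next cycle.** Section 6.3.2 asks for adverse events to have come down to grade 1 or less, with the same exception: "or within 1 grade of starting values for pre-existing laboratory abnormalities".

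**Entry limits.** Section 3.1.4.3 limits ANC, platelets, AST and creatinine, and requires "adequate liver function with total bilirubin" of no more than 2.0 mg/dl. It sets no limit for ALT, alkaline phosphatase or other chemistries.

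**The concern.** A hold protects a patient only if it ends at a better value than the one that started it. The alternative release moves upward with the screening grade, and the trigger stays at grade 3. At some screening grade the two must meet, and from there the hold can end without any change in the patient.

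Section 2.6.1 names hepatotoxicity as a major side effect of 5-FC, and section 6.2.3.1 lists hepatic necrosis with possible fatal outcome. Liver tests are also the main group governed by the catch-all rows. What is at stake is re-treatment while a grade 3 laboratory toxicity is unresolved, in a trial whose primary purpose is to characterize safety.

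**Working it through.** No figure in the plan needs reproducing; this is a check of a decision rule.

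**Step 1. Release level by screening grade.** Let b be the screening grade of the same test. From 6.3.1.2 and the catch-all rows, the highest grade at which a hold may end is 1 if b = 0, and b + 1 if b is 1 or more. The trigger is grade 3 or 4.

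| Screening grade b | Highest release grade | Grade 3 hold | Grade 4 hold |
|---|---|---|---|
| 0 | 1 | ends below trigger | ends at grade 1 |
| 1 | 1 + 1 = 2 | ends below trigger | ends at grade 2 |
| 2 | 2 + 1 = 3 | **release equals trigger** | ends at grade 3 |

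The overlap comes from the added grade. Section 6.3.1.2 already mentions return to baseline, which for b = 2 would be grade 2, one below the trigger. That comparison only locates the source of the overlap.

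**Step 2. Does another rule catch it?**
- *6.3.2, start of cycle:* it carries the same allowance. The other criteria visible there are ANC and platelets; the list breaks off after the platelet item in the available text, so a further criterion cannot be ruled out.
- *6.3.1.7 and 5.8.2, permanent discontinuation:* these apply when the criteria to resume are not met in time (14 days in 6.3.1.7). If the criteria are met when the hold begins, that point is not reached.
- *Table 6.3.4, combination-attributed grade 3, first event:* the pre-hold dose resumes if the event resolves within 7 days. If 6.3.1.2 defines resolution, an unchanged grade 3 value could qualify.

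**Step 3. Which holds are outside the problem?** Platelet holds end at 100 × 10⁹/L or more, and neutrophil holds at an ANC of 1.0 × 10⁹/L or more. The electrolyte row leaves continuation to the investigator, and the renal rows change the dosing interval. None of these uses the catch-all release.

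**Step 4. Can a patient enter at grade 2?** For ALT and alkaline phosphatase, 3.1.4.3 sets no barrier. For AST and bilirubin the answer depends on grade cut-offs that the protocol does not print:
- AST is allowed up to 4 × ULN. That includes grade 2 values if grade 2 starts anywhere below 4 × ULN (assumed starts of 2, 2.5, 3 and 3.5 all qualify; 4 does not).
- Bilirubin of 2.0 mg/dl is 2.0/1.0 = 2.0 × ULN to 2.0/1.4 = 1.43 × ULN for an assumed ULN of 1.0 to 1.4 mg/dl. It exceeds an assumed cut-off of 1.5 × ULN for a ULN of 1.0 to 1.3.

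**Step 5. How many patients?** The documents give no prevalence. If 5% to 20% of the expected 15 to 18 patients had one grade 2 chemistry value at screening (assumption), that is 0.05 × 15 = 0.75 to 0.20 × 18 = 3.6 patients. The rule matters only if the same test then rises to grade 3 or 4 through treatment. With an assumed chance of 10% to 20%, the expected number is 0.75 × 0.10 = 0.075 to 3.6 × 0.20 = 0.72 patients.

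**The case against.** **The wording may already require improvement.** Section 6.3.1.2 speaks of a toxicity that resolves, and 6.3.2 of events that have improved. An unchanged grade 3 value has arguably done neither. This is a fair reading, and it makes the problem partly one of ambiguity. The text does not say that improvement from the triggering grade is needed, and even on this reading a grade 4 event may be released at grade 3.

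**Resumption usually carries a penalty.** For events attributed only to 5-FC in a patient not on leucovorin, the row reads "Restart treatment with a 25% decrease in 5-FC from the pre-hold dose"; a patient on leucovorin first loses the leucovorin. NSC-only events bring a 25% NSC reduction. Grade 4 events attributed to NSCs alone or to the combination also need MRI evidence of benefit. More than two dose reductions end treatment. This stands and limits the exposure, but it does not restore the hold. A first combination-attributed grade 3 event that resolves within 7 days has no penalty.

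**The allowance is permissive and looks deliberate.** It is worded as an option, appears twice, and 5.8.2 defers to section 6.3. Section 6.3.1.5 lets an investigator hold longer with written approval. All true, but this relies on discretion where the written rule is silent.

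**Eligibility is tighter than 3.1.4.3 suggests.** Exclusion 3.2.2 removes patients with unresolved toxicity from earlier treatment, and every patient has had radiation and temozolomide. This shrinks the group; abnormalities from other causes remain possible.

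**Stronger readings to avoid.** A reader might infer that anyone entering with an abnormal laboratory value loses the protection of the hold. Step 1 shows otherwise: a grade 1 baseline still releases below the trigger. A reader might take 1 to 4 patients as the number affected; that range rests on an assumed prevalence and counts abnormal baselines only. A reader might also infer a distorted DLT count. Item 8 in section 5.5 counts grade 3 toxicity persisting beyond 7 days whether or not treatment is held, so early release hides no DLT, and the documents give no basis for a direction or size of bias.

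**Conclusion.** The point holds in a narrow form. For non-hematologic laboratory toxicities under the catch-all rows of Table 6.3.4, chiefly liver tests, a grade 2 screening value in the same test makes the alternative release level coincide with the grade 3 hold trigger. The literal rule then lets a hold end with no improvement, lets a grade 4 event end its hold at grade 3, and bypasses the time limit on unresolved toxicity.

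This conclusion needs only the text and the sum 2 + 1 = 3. It assumes that release does not require improvement from the triggering grade, which the protocol leaves unstated. That a grade 2 baseline can enter rests on the absence of ALT and alkaline phosphatase limits; the AST and bilirubin routes depend on the assumed cut-offs above. The illustrated expectation of fewer than one affected patient rests wholly on assumed rates. The point deserves correction because a written safety rule can cancel itself, even though few patients are likely to meet it.

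**What to change.** The sponsor should reconcile 6.3.1.2 and the parenthesis in 6.3.2 with 5.8.2 and the catch-all rows of Table 6.3.4. The text should state two things:

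- how the baseline allowance operates when one grade above the screening value equals the grade that triggers the hold;
- whether resolution, for the purpose of ending a hold or starting a cycle, requires improvement from the triggering grade.

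The release rule itself is for the investigators to set. The cost is about one sentence in each of the two sections. The downside is that, depending on what is decided, a few patients with abnormal screening values may be held longer.

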### **6.3.2 Start of Cycle Criteria**

In order to proceed with the next cycle of study treatment:

- adverse events (except for alopecia) that occurred in the preceding cycle must have improved to a CTCAE v 4.0 grade  $\leq 1$  (or within 1 grade of starting values for pre-existing laboratory abnormalities),
- ANC must be  $\geq 1500$  cells/mm $^3$ ,
- platelet count  $\geq 100,000$  cells/mm $^3$ , and

